12.3 Appendix 3: Instructions for Subjects Moving from Protocol v1.0 to Protocol v2.0

Visit Schedule

Subjects who have entered the study under protocol v1.0, upon signing the updated informed consent, adapted their visit frequency according to [Table 1](#) Schedule of Assessments. For example, if the subject signs the informed consent for protocol v2.0 at scheduled week 3 (according to protocol v1.0), subject will attend clinic at week 4, week 6 and all subsequent visits as per Schedule of Assessments.

Dosing Instructions for Subjects Moving from Protocol v1.0 to Protocol v2.0 Dosing

Study drug will be dosed TIW throughout the Treatment Period, unless otherwise specified.

Subjects who have entered the study under protocol version 1.0 should, upon signing the updated informed consent, adapt their dose frequency and dose amount. At this visit it is first determined if the subject would need a dose titration according to the dose adjustment rules as per Section [5.1.2](#). Once that is established, patients are converted per the below instructions. The dose assigned must not exceed the maximum allowed dose of 3.0 mg/kg bodyweight or 300 mg per administration, whichever is lower. For subjects on permanent dialysis dose assigned must not exceed 3.0 mg/kg (based on dry weight in HD subjects and weight minus abdominal fluid based on last filling in peritoneal dialysis subjects) or 400 mg per administration, whichever is lower.

- a) Subjects in the correction period or maintenance period on TIW dosing, will continue on TIW dosing for the remainder of the treatment period. If needed their dose will be adjusted according to the conversion table below, at the visit when the updated informed consent is signed.

Current TIW dose (mg)	20	40	50	70	100	120	150	200	250	300	350	400
If no dose titration needed	20	40	50	70	100	100	150	200	250	300	300	300
If up titration needed*	40	50	70	100	150	150	200	250	300	300	300	300
If down titration needed*	#	20	40	50	70	100	100	150	200	250	300	300

- b) Subjects in the maintenance period on BIW dosing will change to TIW dosing immediately, per the conversion table below, at the visit when the updated informed consent is signed.

Current BIW maintenance dose (mg)	20	40	50	70	100	120	150	200	250	300	350	400
If no dose titration needed	20	20	40	50	70	70	100	150	150	200	250	250
If up titration needed*	20	40	40	70	70	100	150	150	200	250	250	300
If down titration needed*	#	20	20	40	50	70	70	100	150	150	200	200

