- c) Subjects in the maintenance period on QW dosing will change to TIW dosing immediately, per the conversion table below, at the visit when the updated informed consent is signed.

Current QW maintenance dose (mg)	20	40	50	70	100	120	150	200	250	300	350	400
If no dose titration needed	20	20	20	20	40	40	50	70	70	100	100	150
If up titration needed*	20	20	20	40	40	50	70	70	100	100	150	150
If down titration needed*	#	#	20	20	20	40	40	50	70	70	100	100

* Up or down titrations were only applicable when the criteria for dose adjustment has been met

Contact the medical monitor if down titration is needed

Note: There are no adaptations to dose frequency or dose amount for subjects moving from Protocol v2.0 to Protocol v2.1.

ESA Rescue Therapy

Protocol v2.0 allows subjects to receive ESA rescue treatment twice. If a third ESA treatment is required the subject will be discontinued from the study treatment.

If, upon implementation of protocol v2.0, a subject has already received 3 or more ESA treatments (under protocol v1.0) they can initially continue in the study. The subject will however, be discontinued from study treatment if a further ESA rescue treatment is required.

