- Kit strength, kit treatment, kit dispensed, date of kit dispensed, kit strength total number of tablets dispensed
- Kit returned, returned date, total number of tablets returned

For each kit, the following will be calculated:

- Start Day of Exposure for each kit: study day kit dispensed
- End Day of Exposure for each kit: study day kit returned – 1 Day
- Amount dispensed for each kit: kit strength x number of tablets dispensed
- Amount returned for each kit: kit strength x number of tablets returned
- Amount consumed for each kit: amount dispensed – amount returned
- Daily consumed dose for each kit : amount consumed/(end day of exposure-start day of exposure +1)

The same methodology as described for Amount Prescribed (planned) Medication will apply to calculate amount of consumed medication for each time period by summing up the different daily consumed amount of the different kits on a given day (subjects will be dispensed more than one kit on a given visit).

In addition, amount of consumed medication in mg/kg will be calculated.

Compliance

Compliance will be calculated for the time periods defined in Amount of Prescribed (planned) Medication. Compliance in % will be calculated for each time period (not reported cumulatively) as:

$$\frac{\text{Amount consumed during time period}}{\text{Amount prescribed during time period}} \times 100$$

The following compliance categories will be defined:

- less than 50% (significant drug noncompliance)
- at least 50%, less than 75% (moderate drug noncompliance)
- at least 75%, less than 125% (acceptable compliance)
- greater or equal 125% (drug over compliance)
- unknown

Dose Changes

Dosing changes are collected in the Study Drug - Dosing Decisions eCRF.

- A dose change is the change in the number of milligrams on the dose per intake (for example from 200 mg to 250 mg).

For example a change from 200 TIW to 250 TIW is a change of 600 mg to 750 mg per week which is regarded as a change in intake dose.

For each subject the total number of dose changes will be calculated.

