7.3.1 Exposure

The following information on drug exposure will be presented by treatment arm and overall, for the SAF.

Exposure related variables are defined in Section [6.5.4](#)

Descriptive statistics will be produced for:

- The amount of drug (roxadustat and placebo) the subject was exposed to during the treatment period (in mg and in mg/kg), by month, during the first 24, 36, 52 weeks and overall;
- Number and percentage of subjects with dose increases, decreases or interruptions during the treatment period.

Duration of exposure will be summarized in two ways:

- Descriptive statistics will be presented overall, during the first 24 weeks, 36 weeks and 52 weeks;
- Exposure time will be categorized overall, and by treatment period, according to the following categories (and frequency tabulations):
 - Less than 2 weeks
 - At least 2 weeks, less than 4 weeks
 - At least 4 weeks, less than 12 weeks
 - At least 12 weeks, less than 24 weeks

- At least 24 weeks, less than 36 weeks
- At least 36 weeks, less than 52 weeks
- At least 52 weeks, less than 78 weeks
- 78 weeks or more
- Unknown.

Box-plots of monthly dose and monthly dose/kg by month will be produced by treatment arm (roxadustat and placebo).

Study drug medication will also be listed showing for each subject and each visit the dispensed kit numbers and the actual medication in each kit. For instance, if a subject randomized to placebo, at one visit was mistakenly dispensed a kit containing roxadustat then the listing will show that roxadustat was given to the subject on the intended visit.

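### SAP 6.5.4 defines a dose change by milligrams per intake, so applied literally it counts the v1.0-to-v2.0 switch to TIW dosing, mostly as a decrease, even with no titration or an up-titration

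*SAP*

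**What the plan says.** SAP 6.5.4 (Dose Changes) gives the rule: "A dose change is the change in the number of milligrams on the dose per intake". Its one illustration keeps the frequency fixed: "a change from 200 TIW to 250 TIW is a change of 600 mg to 750 mg per week". It then adds: "For each subject the total number of dose changes will be calculated". SAP 7.3.1 plans, for the safety set and by arm: "Number and percentage of subjects with dose increases, decreases or interruptions during the treatment period".

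Protocol Appendix 3 (section 12.3) applies to subjects who entered under v1.0. Part b says: "Subjects in the maintenance period on BIW dosing will change to TIW dosing immediately, per the conversion table below". Part c says: "Subjects in the maintenance period on QW dosing will change to TIW dosing immediately, per the conversion table below". Each table lists 12 current doses and gives the new TIW dose for no titration, up-titration and down-titration.

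Neither SAP section excludes or flags this conversion, and SAP 6.5.4 pools subjects from both protocol versions into roxadustat and placebo. Earlier in the same section, the recorded frequency is used to derive the prescribed weekly dose for subjects randomized before v2.0. It is not used in the dose-change rule.

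**The concern.** Going from one or two intakes a week to three usually means fewer milligrams per intake for a similar weekly amount. A rule that sees only the intake reads that as a dose change, usually downward. A subject for whom no titration was decided gains a change. A subject whose dose was raised at the same visit is either counted in the wrong direction or not counted at all.

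The SAP's example cannot reveal this, because frequency is TIW on both sides.

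Two outputs are at stake: the per-subject number of dose changes, and the by-arm table of subjects with increases and decreases. The effect need not be balanced. Under v1.0, all arms were dosed TIW in the correction period (SAP Table 9). QW and BIW occurred only in maintenance, which a subject enters after Hb correction, and roxadustat is expected to achieve correction more often than placebo.

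**Working it through.** **The SAP's own figure.** Weekly dose = dose per intake × intakes per week. 200 × 3 = 600 mg and 250 × 3 = 750 mg, as the SAP states.

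**Inputs from Protocol Appendix 3 (mg).** Current doses are 20, 40, 50, 70, 100, 120, 150, 200, 250, 300, 350, 400. The corresponding new TIW doses are:

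- BIW, no titration: 20, 20, 40, 50, 70, 70, 100, 150, 150, 200, 250, 250
- BIW, up-titration: 20, 40, 40, 70, 70, 100, 150, 150, 200, 250, 250, 300
- QW, no titration: 20, 20, 20, 20, 40, 40, 50, 70, 70, 100, 100, 150
- QW, up-titration: 20, 20, 20, 40, 40, 50, 70, 70, 100, 100, 150, 150

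**Classification of each cell.** Per intake: sign of (new − current). Weekly: sign of (3 × new − f × current), with f = 2 for BIW and 1 for QW.

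| Row | Per intake: down / same / up | Weekly: down / same / up |
|---|---|---|
| BIW, no titration | 11 / 1 / 0 | 4 / 2 / 6 |
| QW, no titration | 11 / 1 / 0 | 3 / 3 / 6 |
| No titration, total | 22 / 2 / 0 | 7 / 5 / 12 |
| BIW, up-titration | 8 / 4 / 0 | 0 / 0 / 12 |
| QW, up-titration | 11 / 1 / 0 | 0 / 1 / 11 |
| Up-titration, total | 19 / 5 / 0 | 0 / 1 / 23 |

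**Examples, both up-titrated.** BIW 100 mg to TIW 70 mg: the intake falls from 100 to 70, while the week goes from 2 × 100 = 200 to 3 × 70 = 210. QW 150 mg to TIW 70 mg: the intake falls from 150 to 70, while the week goes from 150 to 210.

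**What this does to the counts.**

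- No-titration rows: 22 of 24 cells add a dose change that nobody decided. In 7 of the 22 the weekly dose also falls, so in 22 − 7 = 15 the per-intake decrease has no weekly counterpart.
- Up-titration rows: 19 cells record one change in the wrong direction. The other 24 − 19 = 5 (BIW 20, 40, 70 and 150 mg; QW 20 mg) record no change at all.
- TIW conversion table: the no-titration cells at 120, 350 and 400 mg also step down. The weekly dose falls with them, so the two measures agree there.

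**Split between arms (illustration only).** SAP 3.2.3 gives v1.0 allocation as 2:2:2:1:1:1, which is 2:1 overall with two thirds of each treatment group assigned QW or BIW maintenance. Let r and p be the proportions reaching maintenance on roxadustat and placebo. The roxadustat share of converted subjects is 2r / (2r + p).

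- r = p: 2/3 = 67%
- 50% and 25%: 1.00 / 1.25 = 80%
- 65% and 25% (planning response rates, SAP section 4): 1.30 / 1.55 = 84%
- 65% and 10%: 1.30 / 1.40 = 93%

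**The case against.** The strongest reply is that SAP 6.5.4 defines a change and a total but never says how direction is derived. SAP 7.3.1 does not tie its increases and decreases to the per-intake rule. Dose changes come from the Dosing Decisions eCRF, which may record the direction of titration, and the table specifications are a separate document. This stands: the effect on the 7.3.1 table is conditional. The effect on the count of changes is not, although 7.3.1 names no table for that count.

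A reader might go further and infer that roxadustat will appear to have its dose cut much more often, for example in about 43% of v1.0 roxadustat subjects (2/3 × 65%) against 17% of placebo (2/3 × 25%). The documents do not support that as an estimate:

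- The planning rates are a minimum of 65% and a maximum of 25%, so 43% is not a ceiling.
- Hb response over 24 weeks, without prior rescue and with its own criterion at low baseline Hb, is not the same as being in QW or BIW maintenance on the day of the switch.
- The figures count converted subjects, not misclassified ones. Down-titrations at conversion are genuine decisions.
- The 7.3.1 table counts a subject once for any decrease. Protocol 2.2.2 expects weekly dose to fall by 22% to 35% after response through smaller single doses, so many converted subjects may be in that row already.
- The conversion cells are not weighted by how many subjects were at each dose.

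It is also fair that dose intensity can be seen elsewhere. SAP 7.3.1 summarizes the amount of drug by month in mg and mg/kg, and SAP 7.9 reports average weekly dose by v1.0 frequency group up to the switch. Those outputs limit the harm, but they do not correct the count.

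**Conclusion.** The point holds as a minor one. The rule as written registers the mandated frequency conversion as a per-intake decrease in 22 of 24 no-titration cells and 19 of 24 up-titration cells, and it cannot register an up-titration made at a BIW or QW conversion as an increase. The number of dose changes per subject is therefore distorted. The table of increases and decreases is distorted only if direction is taken from milligrams per intake.

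That converted subjects are mostly on roxadustat is probable, not shown. It rests on the 2:1 allocation and on roxadustat subjects reaching Hb correction at least as often as placebo subjects. The number of v1.0 subjects converted is not given, so the effect on the pooled table cannot be sized. No efficacy test, alpha or power is touched. Nothing here bears on which dose or conversion is right.

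**What to change.** Amend SAP 6.5.4 as follows:

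- Flag the v1.0-to-v2.0 conversion visit.
- Do not count the frequency conversion itself as a dose change.
- Report conversions separately, by arm.
- If the Dosing Decisions eCRF records the titration decision (up, down or none) at that visit, count only that decision. Whether it does should be confirmed.
- State how direction is derived for the table in 7.3.1.

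Reclassifying the conversion visit by prescribed weekly dose is not a substitute. Rounding to the fixed dose steps would label 12 of the 24 no-titration cells as increases and 7 as decreases.

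The cost is a sentence or two in the SAP and one programming flag.

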7 STATISTICAL METHODOLOGY

7.1 General Considerations

- All statistical comparisons will be made using two sided tests at the $\alpha=0.05$ significance level unless specifically stated otherwise. Null hypotheses for superiority testing will be of no treatment difference and corresponding alternative hypothesis will be two-sided. Null hypotheses for non-inferiority testing will be of inferiority of roxadustat treatment and will be one-sided at the $\alpha=0.025$.
- All data processing, summarization, and analyses will be performed using SAS® Version 9.3 (SAS Enterprise Guide 4.3) or higher. Specifications for tables, data listings and figures (TLFs) formats can be found in the TLF Specifications for this study.
- All data will be summarized by treatment arm (roxadustat and placebo) and for the total, unless specified otherwise.
- For continuous variables that are recorded as “< X” or “> X”, the value of “X” will be used in the calculation of summary statistics. The original values will be used for the listings.
- All percentages will be rounded to one decimal place and lined up by the decimal place. The percentage will be suppressed when the count is zero.
- Any p-values will be rounded to four decimal places and will be presented as ‘< 0.0001’ if they are less than 0.0001 after rounding.
- For continuous variables, descriptive statistics will include the number of subjects (n), mean, standard deviation, median, minimum and maximum. Frequencies and percentages will be displayed for categorical data. Percentages by categories will be based on the number of subjects with no missing data, i.e., will add up to 100%. Number of missing values will be shown in the frequencies tables
- All data included in summary tables, inferential analyses or figures will also be listed.
- Listings will be done on all randomized subjects and all assessments (all collected data in the eCRF will be listed except the physical examination data).
- Model checking will be performed using graphical outputs provided by the SAS procedures.

For the definition of subgroups of interest please refer to Section [7.8](#).

7.2 Study Population

For this section, unless specified otherwise, PPS refers to the analysis set which excludes from the FAS all the subjects criteria listed in [Table 3](#) See Section [5.3](#) for more details.

7.2.1 Disposition of Subjects

The following subject data will be summarized and presented:

- Number and percentage of subjects with informed consent, who discontinued before randomization and randomized (overall only);

- Number and percentage of subjects randomized in each analysis set, by treatment arm and overall;
- Number and percentage of subjects who completed and discontinued treatment in each period (primary treatment period and extended treatment period), by primary reason for treatment discontinuation and by treatment arm for All Randomized, SAF, FAS and PPS;
- Number and percentage of subjects who completed and discontinued the study, by primary reason for study discontinuation and by treatment arm for All Randomized and SAF;
- Number and percentage of subjects who completed and discontinued the post study follow-up period for All Randomized and SAF, and
- Number and percentage of subjects excluded from PPS by reason for exclusion defined in Section 5.3 by treatment arm for the FAS.

The following data will be presented graphically by treatment arm for the FAS and the SAF:

- Treatment discontinuation by reason using bar chart;
- Treatment discontinuation by time interval and reason using bar chart; and
- Time to treatment discontinuation using a Kaplan-Meier plot.

In addition, the following graphs will be done by treatment arm, for the FAS and PPS:

- Treatment discontinuation for lack of efficacy using a cumulative incidence plot;
- Treatment discontinuation for adverse event using a cumulative incidence plot.
- Treatment discontinuation for withdrawal by subject using a cumulative incidence plot.

Time intervals will be analyzed using the following categories:

- Less than 2 weeks
- At least 2 weeks, less than 4 weeks
- At least 4 weeks, less than 12 weeks
- At least 12 weeks, less than 24 weeks
- At least 24 weeks, less than 36 weeks
- At least 36 weeks, less than 52 weeks
- At least 52 weeks, less than 78 weeks
- 78 weeks or more
- Unknown.

In addition, the randomization stratification strata from both sources (CRF and IRT) will be reported by treatment arm. Discrepancy between stratification from CRF and IRT will be summarized and the total number of patients with discrepancy overall and for each stratification factor will be provided

Subjects who screened failure will also be listed.

All data collected during the Post-Study Follow up period will be listed by visit (i.e type of contact, subject status and occurrence of overnight hospitalizations).

7.2.2 Protocol Deviations

Protocol deviations, as defined in the study protocol (Section 8.1.6: Protocol Deviations) will be assessed for all randomized subjects. The number and percentage of subjects meeting any criteria will be summarized for each criterion and overall, by treatment arm, as well as by study site. Subjects deviating from a criterion more than once will be counted once for the corresponding criterion. Subjects who have more than one protocol deviation will be counted once in the overall summary. A data listing will be provided by site and subject.

The protocol deviation criteria will be uniquely identified in the summary table and listing. The unique identifiers will be as follows:

- PD1 - Entered into the study even though they did not satisfy entry criteria,
- PD2 - Developed withdrawal criteria during the study and was not withdrawn,
- PD3 - Received wrong treatment or incorrect dose
 - PD3_1- Received wrong treatment kit
 - PD3_2- Received incorrect dose
- PD4 - Received excluded concomitant treatment

7.2.3 Demographic and Other Baseline Characteristics

Demographic and other baseline/screening characteristics will be summarized by descriptive statistics and frequency tabulations.

Number and percentage of subjects randomized in each country and site will be presented for the All Randomized and SAF. Descriptive statistics for age, weight, body mass index (BMI) and height at baseline will be presented. Frequency tabulations for sex and race will be presented. Descriptive statistics and frequency tabulations will also be presented for the subgroup variables presented in Section 7.8. Additionally, demographic and other baseline characteristics will be presented for the following variables:

- Baseline and Screening Hb value as continuous and categorical (≤ 8.0 g/dL versus >8.0 g/dL),
- Baseline and Screening eGFR value as continuous and categorical (< 30 mL/min/1.73 m² versus ≥ 30 mL/min/1.73m², and <10 , $10-<15$, $15-<30$, $30-<45$, $45-<60$, and ≥ 60 mL/min/1.73m²)
- History of previous treatment with ESA: Yes vs. No.

Demographic and baseline characteristics summaries above will be done for the All Randomized, SAF, FAS and PPS. This table will be repeated for subjects randomized after Amendment 2.0 is implemented.

Selected demographics collected at screening will be done on Screen Failure subjects.

All Medical History will be analyzed using the SAF, as described below:

Medical History other than anemia, CKD, cardiovascular disease and targeted medical history are coded in MedDRA, they will be summarized by System Organ Class and Preferred Term.

Anemia history, CKD history, targeted medical history, cardiovascular history, tobacco history and family history of cardiovascular disease will be summarized.

The number and proportion of subjects with each typical symptom for CKD will be described, as well as the number and proportion of subjects with each typical symptom for anemia.

Demographic and baseline data will also be listed.

7.2.4 Previous and Concomitant Medications

Previous and concomitant medications are coded with WHO-DD, and will be summarized by therapeutic subgroup (ATC 2nd level), chemical subgroup (ATC 4th level) and preferred WHO name for the SAF.

Subjects taking the same medication multiple times will be counted once per medication.

Treatment history for anemia will be summarized separately.

Missing dates' imputation rules are detailed in Section [7.11.2](#)

7.3 Study Drugs

Roxadustat (=Investigational Product Medicine) is for oral administration and supplied as red coated oval tablets of 20, 50 and 100 mg. Roxadustat and placebo tablets are identical in size, shape and color to preserve the blinding method.

